### 1.2 COVID-19 ACCOMMODATIONS

The COVID-19 pandemic is expected to have various effects on clinical trials. Due to closure of sites during the COVID-19 pandemic, it is expected that there will be more missing data than usual, more protocol deviations may be observed, changes in patient population may occur, adverse events and concomitant medications may be underreported, and/or treatment interruption may occur. Twenty subjects were enrolled prior to enrollment hold/closures at sites due to the pandemic. These subjects will comprise the pre-pandemic subjects. All other subjects enrolled later will comprise the post-pandemic subjects.

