# 1.2.1 Missing Data

It is known that 3 subjects were unable to provide pharmacokinetic (PK) assessments at the Treatment Phase Week 3 Visit. All other subjects had completed the Treatment Phase Week 3 Visit prior to site closures, and no new subjects were enrolled during the time of site closures. Subjects were unable to attend visits during the Optional Extension Phase. Visit windows will be expanded to allow for out-of-window visits to be slotted to a scheduled visit.

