# 1.2.4 Impact on Safety Evaluation

In order to assess whether adverse events (AEs) were underreported during site closures, the rate of AEs will be calculated pre- and post-pandemic for those subjects who remained in the study during site closures. No assessment of underreporting of concomitant medications is planned.

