#### 9.6 ASSESSMENT WINDOWS

For any data summarized by scheduled visit, an analysis visit window will be used. In the protocol, the visit window for the Week 3 Visit and the End of Study Visit is  $\pm 3$  days. The visit window for the Optional Extension Phase Visits is  $\pm 5$  days. In order to allow slotting of discontinuation visits and visits outside the planned schedule, the visit windows have been expanded for analysis purposes. The scheduled visits, as recorded on the eCRFs, and the corresponding target days and study day intervals are specified in Table 9-2. The analysis visit will be derived based on the information specified in Table 9-2.

**Table 9-2** Assessment Windows for Scheduled Visits

Visit	Target Study Day	Study Day Interval	
ECGs			
Baseline	1 Study Day ≤1 (prior to the date of the first dose)		
End of Study Visit		Last assessment after Study Day 1	
	PC	Q-ITD	
Baseline	1	Study Day ≤1 (prior to the date of the first dose)	
Week 3	22	1< Study Day ≤ Last assessment day during Treatment Phase	
End of Study Visit		Last assessment after Study Day 1	
	PAH-S	YMPACT	
Baseline	1	Study Day ≤1 (prior to date of the first dose)	
Week 3	22	1< Study Day ≤ Last assessment day during Treatment Phase	
Week 11	78	Any assessment during Optional Extension Phase	
End of Study Visit		Last assessment after Study Day 1	
Clini	cal laboratory asses	ssments, vital signs, 6MWT	
Baseline	1	Study Day ≤1 (prior to date of the first dose)	
Week 3	22	1< Study Day ≤ Last assessment day during Treatment Phase	
Week 11	78	Last assessment day during Treatment Phase < Study Day ≤106	
Subsequent weeks (every 8 weeks after Week 11)	Week*7+1	Target Study Day-28 < Study Day ≤ Target Study Day+28 or last assessment day during the Optional Extension Phase for final visit	
End of Study Visit		Last assessment in the study	

Abbreviations: 6MWT, 6-Minute Walk Test; ECG, electrocardiogram; PAH-SYMPACT, Pulmonary Arterial Hypertension-Symptoms and Impact; PQ-ITD, Preference Questionnaire for Inhaled Treprostinil Devices; \*, times. Note: Study Day = (Assessment Date) – (First Dosing Date) +1

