#### 12.2 ADVERSE EVENTS

All AEs will be coded to the appropriate PT and SOC using MedDRA. AEs will be listed by TreT dose including all details recorded on the eCRF plus an indicator of whether the event was treatment emergent. Treatment-emergent AEs are those AEs with an onset date equal to or after the start date of TreT. The AE listings will include the AE verbatim term and its corresponding PT and SOC.

The AE summaries will be limited to include only treatment-emergent AEs and will be prepared for the Treatment Phase and the combined Treatment Phase and Optional Extension Phase. The non-treatment-emergent AEs (the AEs occur after signing the Informed Consent Form but before receiving TreT) will be listed but not included in summary tables.

All summaries will include the number and percentage of subjects experiencing each type of AE and the total number of each type of AE, in order of overall frequency and/or SOC. Serious adverse events (SAEs) and non-serious AEs will also be summarized by SOC and PT.

The total number of AEs and the AE rates will be calculated and summarized for each display, as appropriate. The AE rate will be calculated as the total number of AEs divided by the total patient years of exposure to study drug per TreT dose.

AEs possibly or probably related to study drug will be summarized. An AE summary by severity (mild, moderate, and severe) will also be provided.

Separate listings and summary tables will be provided for all SAEs, AEs leading to the discontinuation of study drug, and all deaths during the study (if data permit). For the listing

of deaths, information for all subjects who die during the study period from Baseline to the end of the study (including 30 days after the last TreT dose) will be included.

To assess possible underreporting of AEs, an additional summary will be created for AEs by time of enrollment: pre- or post-pandemic.

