# 15 APPENDICES

# 15.1 LIST OF TABLES

Table Number	Table Title
14.1.1	Summary of Subject Accountability
14.1.2	Summary of TreT Exposure
14.1.3.1	Summary of Entry Criteria Violations
14.1.3.2	Summary of Protocol Deviations
14.1.4	Summary of Demographics
14.1.4.1	Summary of Demographics by Time of Enrollment
14.1.5	Summary of Medical History
14.1.6	Summary of PAH History
14.1.6.1	Summary of PAH History by Time of Enrollment
14.1.7.1	Summary of Concomitant Medications Ongoing at Baseline
14.1.7.2	Summary of Concomitant Medications Added during the Treatment Phase
14.1.7.3	Summary of Concomitant Medications Added during the Optional Extension Phase
14.1.7.4	Summary of Background PAH Medications
14.1.7.5	Summary of Tyvaso Medication History
14.1.8	Summary of TreT Dosing
14.1.9	Summary of TreT Treatment Compliance
14.2.1.1	Summary and Analysis of 6MWD (meter) during Treatment Phase
14.2.1.2	Summary of 6MWD (meter) during Optional Extension Phase
14.2.2.1	Summary of Preference Questionnaire for Inhaled Treprostinil Devices
14.2.2.2	Analysis of Preference Questionnaire for Inhaled Treprostinil Devices
14.2.3	Summary and Analysis of PAH-SYMPACT Questionnaire
14.3.1.1	Overall Summary of Adverse Events
14.3.1.2	Summary of Adverse Events by System Organ Class and Preferred Term
14.3.1.3	Summary of Adverse Events by Preferred Term
14.3.1.4	Summary of Deaths
14.3.1.5	Summary of Serious Adverse Events by System Organ Class and Preferred Term
14.3.1.6	Summary of Non-serious Adverse Events by System Organ Class and Preferred Term
14.3.1.7	Summary of Adverse Events Probably or Possibly Related to Study Drug by System Organ Class and Preferred Term
14.3.1.8	Summary of Adverse Events Leading to Permanent Discontinuation of Study Drug by Preferred Term
14.3.1.9	Summary of Adverse Events by System Organ Class, Preferred Term, and Severity
14.3.1.10	Listing of Deaths
14.3.1.11	Listing of Serious Adverse Events

Table Number	Table Title
14.3.1.12	Summary of Adverse Events by System Organ Class, Preferred Term, and Time of Enrollment
14.3.2.1	Summary of Clinical Chemistry
14.3.2.2	Summary of Clinical Chemistry Shift from Baseline
14.3.2.3	Summary of Hematology
14.3.2.4	Summary of Hematology Shift from Baseline
14.3.3.1	Summary of Vital Signs
14.3.3.2	Summary of Electrocardiogram Parameters
14.3.3.3	Summary of Electrocardiogram Categorical Results

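### SAP 1.2.4 sets no usable periods for the check on AE underreporting during site closures, and the enrollment-cohort split in 12.2 cannot isolate closure time

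*SAP*

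**What the plan says.** SAP 1.2 names AE underreporting as a possible effect of the pandemic and defines two groups by date of enrollment. For the first: "Twenty subjects were enrolled prior to enrollment hold/closures at sites due to the pandemic"; these are the pre-pandemic subjects. For the second: "All other subjects enrolled later will comprise the post-pandemic subjects".

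SAP 1.2.1 reports that 3 subjects could not give Week 3 PK assessments. It continues: "All other subjects had completed the Treatment Phase Week 3 Visit prior to site closures, and no new subjects were enrolled" while sites were closed.

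Two sections then address underreporting:

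- SAP 1.2.4, on underreporting during site closures: "the rate of AEs will be calculated pre- and post-pandemic for those subjects who remained in the study during site closures".
- SAP 12.2: "To assess possible underreporting of AEs, an additional summary will be created for AEs by time of enrollment: pre- or post-pandemic". The matching entry in SAP 15.1 is Table 14.3.1.12, "Summary of Adverse Events by System Organ Class, Preferred Term, and Time of Enrollment".

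SAP 12.2 defines the AE rate as events over patient-years of exposure, per TreT dose, with no calendar split. AE summaries "will be prepared for the Treatment Phase and the combined Treatment Phase and Optional Extension Phase".

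**The concern.** Both sections state the same purpose but describe different comparisons. Section 1.2.4 takes the people who were in the study when sites closed, which makes sense only as a comparison of calendar periods. Section 12.2 compares people by when they enrolled.

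Enrollment cohort suits the question in SAP 1.2.3, whether the population changed. It does not suit the question whether events went unrecorded while sites were shut. A programmer working from 12.2 and 15.1 has a defined display for the cohort split, but no periods, dates or display for the 1.2.4 rates.

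Safety is the primary objective, and closure time falls mostly in the Optional Extension Phase, which serves the long-term safety objective. If the cohort table is read as the underreporting check, it can reassure wrongly or raise a false alarm.

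**Working it through.** The plan gives no figure for this check, so there is none to reproduce. Steps 1 and 2 use the text alone. Steps 3 to 6 are illustrations, because the documents give no closure dates, exposure by period or AE rates.

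**1. Can the enrollment definition be applied to the 1.2.4 subjects?** Nobody enrolled during closures (1.2.1). Anyone in the study during closures had therefore enrolled before them and is one of the 20 pre-pandemic subjects (1.2). The number of 1.2.4 subjects in the post-pandemic cohort is 0. Only a calendar-period reading of 1.2.4 works, and the SAP sets no periods. It does not say whether closure time counts as post-pandemic.

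**2. What does the 12.2 split compare?** One side holds all time of the 20 earlier subjects: before, during and after closure. The other holds later enrollees, 45 − 20 = 25 if the planned total is reached, with no time in that closure period.

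**3. Dilution.** Let f be the closure share of the earlier cohort's exposure, u the fraction of closure-period AEs not reported, and c the true AE rate ratio, earlier to later cohort. With a constant AE rate within each cohort:

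- cohort ratio = c × (1 − f × u)
- within-subject ratio, closure to open time = 1 − u

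With u = 0.50 the within-subject ratio is 0.50. The cohort ratios are:

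| c | f = 0.10 | f = 0.30 | f = 0.50 |
|---|---|---|---|
| 1 | 0.95 | 0.85 | 0.75 |
| 0.8 | 0.76 | 0.68 | 0.60 |
| 1.25 | 1.19 | 1.06 | 0.94 |

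For other u with c = 1, f from 0.10 to 0.50 gives 0.975 to 0.875 at u = 0.25 and 0.925 to 0.625 at u = 0.75. A modest case-mix difference (the c = 1.25 row) can hide the deficit or reverse its direction.

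**4. Treatment Phase display.** At most 3 of the 20 were still short of the Week 3 Visit at closure. If each subject has about 21 days, f is at most (3 × 21)/(20 × 21) = 63/420 = 0.15. This is a ceiling, because all 3 had enrolled before closure. If 7 of their days came earlier, f = (3 × 14)/420 = 0.10. With u = 0.50 and c = 1, the ratio is 0.925 at the ceiling and 0.95 at f = 0.10. The 21 days are an assumption; a longer stay in the phase for these 3 would raise f. Table 9-2 closes the Week 3 window only at "Last assessment day during Treatment Phase", but it slots visit data, not AEs or exposure.

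**5. Combined-phase display, no underreporting.** Suppose the AE rate in the first 3 weeks is twice the later rate. The average rate over t weeks is then (6 + t − 3)/t, in units of the later rate. For assumed exposures, earlier/later cohort, of 20/3, 40/11 and 68/20 weeks:

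- 1.150/2.000 = 0.58
- 1.075/1.273 = 0.84
- 1.044/1.150 = 0.91

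Longer follow-up alone produces an apparent deficit in the earlier cohort.

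**6. The same test on the period comparison.** Suppose the rate in the first 3 weeks is k times the later rate, and X later weeks precede closure. With full reporting, the closure to pre-closure ratio is (3 + X)/(3k + X). For X = 8 it is 11/14 = 0.79 at k = 2 and 11/17 = 0.65 at k = 3. Restricted to time after Week 3, it is 1.00 if the rate is constant from then on. The period comparison is therefore not free of time effects, but these can be footnoted or split out.

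**The case against.** **Nothing was replaced.** A reader might infer that 12.2 supersedes 1.2.4, or that the 1.2.4 rates will not be produced because 15.1 has no table for them. The documents do not support this. Section 12.2 calls its summary additional, and 1.2.4 still stands. The table list is not one-to-one with the text: the subgroup analyses in 9.2 have no table, and the Baseline satisfaction figure planned in 11.2 is missing from 15.3. What remains is that 1.2.4 has no periods, and that 12.2 assigns the same purpose to a comparison that cannot serve it.

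**AE capture continued.** One might also infer that events were in fact lost. The SAP says only that they may be. Protocol 3.3.2.8 requires regular telephone or email contact, and 3.3.2.6 asks subjects to report AEs spontaneously. The size of any underreporting is unknown.

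**The limit of 3 in 20 is narrow.** It holds for on-treatment time up to Week 3. Subjects who decline the extension have 2 further weeks to the End of Study Visit, and the SAP does not say which display holds AEs from that time. It would be wrong to say that only 3 subjects can have closure time in the Treatment Phase display.

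**The stakes are low.** The check is descriptive, and no decision depends on it. Onset dates are recorded, so events could be assigned to periods later. This limits the weight of the point, but a planned check should still be able to answer its own question.

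**Conclusion.** The point holds as a flaw in a minor supporting check. The enrollment definition cannot be applied to the subjects named in 1.2.4; that follows from the SAP's own text. The 12.2 split, followed as written, cannot isolate closure-period underreporting. It dilutes any deficit and mixes it with case mix in both displays, and with time on TreT and titration in the combined-phase display, since titration starts only after the Week 3 assessments.

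The size is illustrative. With half of closure-period AEs unreported, a constant AE rate, equal true rates in the cohorts and closure at 10% to 50% of the earlier cohort's exposure, the cohort ratio is 0.95 to 0.75, against 0.50 within subjects. In the Treatment Phase display the closure share is at most about 0.15 on 21 days each. None of this shows that AEs were missed, and the flaw does not affect the main AE tables.

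**What to change.** - **SAP 1.2.4:** add *Pre-, during- and post-closure are calendar periods set by the closure and reopening dates of each subject's site; AEs are assigned to periods by onset date.*
- **SAP 12.2:** replace the sentence on underreporting with *To assess possible underreporting, AE counts, patient-years and AE rates will be summarized descriptively by pre-, during- and post-closure period for subjects in the study during closure.*
- **SAP 15.1:** list this display, for example as Table 14.3.1.13. Footnote that time on TreT, titration, and interruptions not deducted from exposure (1.2.6) can also move the rates. A further split at Week 3 is optional.
- **Table 14.3.1.12:** keep it, but describe it in 12.2 as a comparison of enrollment cohorts.

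The cost is wording in two sections and one descriptive table. AE onset dates (Protocol 9.2) and TreT dosing dates (SAP 12.1) are already collected. Site closure and reopening dates are not in the documents and must be compiled. With at most 20 subjects the period rates will be imprecise, more so if split at Week 3.

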#### 12.3 CLINICAL LABORATORY ASSESSMENTS

# 12.3.1 Clinical Chemistry and Hematology

Blood for the measurement and evaluation of clinical chemistry and hematology collected at study visits will be used to assess treatment-emergent changes in clinical chemistry and hematological laboratory parameters. Values will be obtained for the parameters listed in Table 12-1.

**Table 12-1** Clinical Laboratory Parameters

Electrolyte Panel Chemistry Panel		Hematology Panel
Bicarbonate	Alanine aminotransferase	Hemoglobin
Chloride	Aspartate aminotransferase	Hematocrit
Potassium	Bilirubin (total and indirect)	Red blood cell count
Sodium	Creatinine	White blood cell count
	Blood urea nitrogen	Platelet count

Values that are "high" or "low" with respect to the reference range provided by the central laboratory will be flagged with an "H" or an "L," respectively. All parameters will be listed for all subjects and assessments, along with their respective "high/low" flags.

Values of these parameters at each visit, and their corresponding changes from Baseline, will be descriptively summarized by TreT dose and overall.

For each parameter, the frequency and percentage of subjects within each TreT dose and overall who had "low," "normal," or "high" Baseline values, then subsequently had "low," "normal," or "high" follow-up values at each visit will be presented in a shift summary.

# 12.3.2 Pregnancy Testing

Women of childbearing potential will undergo a urine pregnancy test at study visits. A listing of pregnancy test results will be provided.

#### 12.4 VITAL SIGNS

All vital sign assessments will be listed for all subjects. This listing will include weight, BMI, heart rate (HR), systolic and diastolic blood pressures, and respiratory rate. The vital sign results at each assessment and changes for each post-Baseline assessment will be descriptively summarized by TreT dose and overall at each visit during the Treatment Phase and Optional Extension Phase.

# 12.5 ELECTROCARDIOGRAMS

All ECG assessments will be listed for all subjects. This listing will include the HR, the ECG interval from the beginning of the QRS complex to the end of the T wave (QT interval), the QT interval corrected for HR (QTc) (calculated using formulas by both Bazett and Fridericia as described in Section 9.5.2), the time between the P wave and the beginning of the QRS complex in ECG (PR interval), the electrocardiographic wave (QRS) duration, ECG results (normal/abnormal), whether there were clinically significant changes from the Screening Visit, whether abnormalities were present, and details and comments on any abnormalities. The ECG results at Baseline and changes for each post-Baseline assessment will be descriptively summarized by TreT dose and overall at each visit during the Treatment Phase and Optional Extension Phase. In addition, for QTc intervals calculated using both the Bazett and Fridericia methods, the number and percent of subjects with values ≥500 msec and the number and percent of subjects with changes from Screening of <30 msec, 30 to <60 msec, and ≥60 msec will be presented. Additionally, each abnormality will be summarized by the number and percentage of subjects reporting at each visit by TreT dose and overall at each visit during the Treatment Phase and Optional Extension Phase.

#### 13 PHARMACOKINETICS

A listing will include the date and time of specimen collection for pharmacokinetics. Details of the analyses of the PK data will be provided in a separate SAP.

# 14 BIOMARKERS AND WHOLE GENOME SEQUENCING

A listing will include the date and time of specimen collection for biomarkers and whole genome sequencing. Details of the analyses of the optional biomarkers and optional whole genome sequencing will be provided in a separate SAP.

# 15 APPENDICES

# 15.1 LIST OF TABLES

Table Number	Table Title
14.1.1	Summary of Subject Accountability
14.1.2	Summary of TreT Exposure
14.1.3.1	Summary of Entry Criteria Violations
14.1.3.2	Summary of Protocol Deviations
14.1.4	Summary of Demographics
14.1.4.1	Summary of Demographics by Time of Enrollment
14.1.5	Summary of Medical History
14.1.6	Summary of PAH History
14.1.6.1	Summary of PAH History by Time of Enrollment
14.1.7.1	Summary of Concomitant Medications Ongoing at Baseline
14.1.7.2	Summary of Concomitant Medications Added during the Treatment Phase
14.1.7.3	Summary of Concomitant Medications Added during the Optional Extension Phase
14.1.7.4	Summary of Background PAH Medications
14.1.7.5	Summary of Tyvaso Medication History
14.1.8	Summary of TreT Dosing
14.1.9	Summary of TreT Treatment Compliance
14.2.1.1	Summary and Analysis of 6MWD (meter) during Treatment Phase
14.2.1.2	Summary of 6MWD (meter) during Optional Extension Phase
14.2.2.1	Summary of Preference Questionnaire for Inhaled Treprostinil Devices
14.2.2.2	Analysis of Preference Questionnaire for Inhaled Treprostinil Devices
14.2.3	Summary and Analysis of PAH-SYMPACT Questionnaire
14.3.1.1	Overall Summary of Adverse Events
14.3.1.2	Summary of Adverse Events by System Organ Class and Preferred Term
14.3.1.3	Summary of Adverse Events by Preferred Term
14.3.1.4	Summary of Deaths
14.3.1.5	Summary of Serious Adverse Events by System Organ Class and Preferred Term
14.3.1.6	Summary of Non-serious Adverse Events by System Organ Class and Preferred Term
14.3.1.7	Summary of Adverse Events Probably or Possibly Related to Study Drug by System Organ Class and Preferred Term
14.3.1.8	Summary of Adverse Events Leading to Permanent Discontinuation of Study Drug by Preferred Term
14.3.1.9	Summary of Adverse Events by System Organ Class, Preferred Term, and Severity
14.3.1.10	Listing of Deaths
14.3.1.11	Listing of Serious Adverse Events

Table Number	Table Title
14.3.1.12	Summary of Adverse Events by System Organ Class, Preferred Term, and Time of Enrollment
14.3.2.1	Summary of Clinical Chemistry
14.3.2.2	Summary of Clinical Chemistry Shift from Baseline
14.3.2.3	Summary of Hematology
14.3.2.4	Summary of Hematology Shift from Baseline
14.3.3.1	Summary of Vital Signs
14.3.3.2	Summary of Electrocardiogram Parameters
14.3.3.3	Summary of Electrocardiogram Categorical Results

# 15.2 LIST OF LISTINGS

Listing Number	Listing Title
16.2.1.1	Subject Disposition
16.2.1.2	Subject Accountability
16.2.2.1	Entry Criteria
16.2.2.2	Protocol Deviations
16.2.4.1	Demographics
16.2.4.2	PAH History
16.2.4.3	Medical History
16.2.4.4	PAH Background Medications
16.2.4.5	Tyvaso Medication History
16.2.4.6	Concomitant Medications
16.2.5	TreT Dosing
16.2.6.1	6-Minute Walk Test
16.2.6.2	Preference Questionnaire – Inhaled Treprostinil Device (Part 1 of 2)
16.2.6.2	Preference Questionnaire – Inhaled Treprostinil Device (Part 2 of 2)
16.2.6.3.1	PAH-SYMPACT Questionnaire (Cardiopulmonary Symptoms)
16.2.6.3.2	PAH-SYMPACT Questionnaire (Cardiovascular Symptoms)
16.2.6.3.3	PAH-SYMPACT Questionnaire (Physical Impacts)
16.2.6.3.4	PAH-SYMPACT Questionnaire (Cognitive/Emotional Impacts)
16.2.7.1	Adverse Events
16.2.7.2	Adverse Events Leading to Discontinuation of TreT
16.2.8.1	Clinical Chemistry
16.2.8.2	Hematology
16.2.8.3	Pregnancy Test Results
16.2.8.4	Other Laboratory Tests
16.2.8.5	Vital Signs
16.2.8.6	ECG Results

